9.1 Subject Completion

A subject will be considered to have completed the study if the subject meets at least 1 of the following criteria:

- 9.1.1 The subject has completed 16 weeks of treatment with study medication with no improvement.
- 9.1.2 The subject died during the study.
 - 9.1.3 The subject withdrew from study including subjects who experience a DLT.
- 9.1.4 The subject experienced an AE that lead to withdrawal from the study.

9.2 Subject Withdrawal from Study

A subject may voluntarily withdraw from study medication or withdraw consent from the study at any time. The investigator may also, at his or her discretion, discontinue a subject from participating in the study at any time. The investigator will record the date and the reason for subject withdrawal from the study.

9.3 Subject Withdrawal from Study Medication

If the subject is permanently withdrawn from treatment with study medication, but does not withdraw consent, the investigator must make every effort to have the subject complete all withdrawal assessments at the time of withdrawal, and complete all scheduled follow-up visits. Treatment with study medication must be discontinued if:

- The subject withdraws consent.
- Further participation would be injurious to the subject's health or well-being in the Investigator's medical judgment.

- The study is terminated.
- Marketing approval of CMML
- The subject becomes pregnant
- The subjects exhibits leukemic transformation (as evidenced by bone marrow blast counts of at least 20%, or peripheral blast counts of at least 20% lasting at least 8 weeks.
- No clinical benefit has been attained after 16 weeks of treatment.
- Evidence of Disease progression according to IWG 2006 criteria.
- a subject experiences a DLT.
- a subject is significantly non-compliant with the requirements of the protocol.
- a subject has an adverse experience that would, in the investigator's judgment, make continued participation in the study an unacceptable risk.

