
Subjects who were not enrolled in the MTD cohort can increase to the MTD after week 16 if the participant still meets the eligibility criteria. Responding patients will be able to continue treatment until marketing approval of ruxolitinib for CMML. **Duration of** Subjects will be followed as per calendar on treatment for 17 weeks. After 17 weeks, subjects who continue on study will be followed monthly. Off study data on AML transformation and Follow-Up overall survival will be updated every 6 months or until death, whichever occurs first. Subjects removed from the study for unacceptable adverse events will be followed until resolution or stabilization of the adverse event. Criteria for Removal from Study Study drug treatment can continue for subjects receiving clinical benefit, unless; one or more withdrawal criteria are met, or at the subject's discretion, or if the study is terminated, or until the marketing approval for CMML *Subject Completion A subject will be considered to have completed the study if the subject meets at least 1 of the following criteria: - The subject has completed 16 weeks of treatment with study medication with no improvement. - The subject died during the study. - The subject withdrew from study including subjects who experience a DLT. - The subject experienced an AE that lead to withdrawal from the study. *Subject Withdrawal from Study A subject may voluntarily withdraw from study medication or withdraw consent from the study at any time. The investigator may also, at his or her discretion, discontinue a subject from participating in the study at any time. The investigator will record the date and the reason for subject withdrawal from the study. *Subject Withdrawal from Study Medication If the subject is permanently withdrawn from treatment with study medication, but does not withdraw consent, the investigator must make every effort to have the subject complete all withdrawal assessments at the time of withdrawal, and complete all scheduled follow-up visits. Treatment with study medication must be discontinued if (Withdrawal Criteria): • No clinical benefit has been attained after 16 weeks of treatment. • Evidence of Disease progression according to IWG 2006 criteria. a subject experiences a DLT. • a subject becomes pregnant. • a subject is significantly non-compliant with the requirements of the protocol; • a subject has an adverse experience that would, in the investigator's judgment, make continued participation in the study an unacceptable risk See calendar page 36 Follow up on study **Statistics Study Design:** This study will use a dose escalation, "rolling 6" design in Phase 1. Subjects will be allocated to starting doses of 10 mg/d to 40mg/d (divided in two equal doses) escalated by 10 mg/day for each cohort according to the predetermined algorithm outlined below in Table 1 (section 6.4). Each cohort will include 6 subjects. After testing the treatment dose on 10 patients in the first stage, the trial will be terminated if 1 or fewer desired respond. If the trial goes on to the second stage, a total of 29 patients will be studied. If the total number responding is less than or equal to 5, the drug is rejected. *Sample Size/Accrual Rate

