3 STUDY ENDPOINTS

3.1 Primary

- 3.1.1 The maximum tolerated dose (MTD) of ruxolitinib for the treatment of CMML. The MTD is defined as the highest dose where less than 33% of subjects experience a drug related predefined dose limited toxicity (DLT).
- 3.1.2 Proportion of subject achieving clinical benefit defined as hematologic improvement, complete remission, partial remission, or stable disease by the IWG 2006 criteria (see appendix B)

- 3.2 Secondary
- **3.2.1** Acute myeloid leukemia (AML) transformation according to WHO criteria.
- **3.2.2** Overall survival (OS).
- **3.2.3** Duration of response.
- 3.2.4 The Myeloproliferative Neoplasms Symptom Assessment Form (MPN-SAF) at baseline and at best response.
- 3.2.5 >50% decrease in splenic length as measured by physical exam if applicable
- **3.2.6** The suppression of pSTAT5 intracellular signaling after ruxolitinib in CMML subjects (pretreatment, at 1-2hr post treatment, cycle 2, cycle 4, and progression.)
- **3.2.7** Determine number of colonies formed in the presence of GM-CSF and/or ruxolitinib (pretreatment and progression) as a future predictor of response.
- 3.2.8 Mutational status in our CMML subjects by sanger sequencing of JAK2, c-CBL, N-RAS, K-RAS,RUNX-1, TET2, SRSF2, EZH2, ASXL1, and DNMT3a (pretreatment and progression).
- 3.2.9 Mutational status of JAK2 tyrosine kinase at time of progression by deep sequencing of JAK2 to include M929I, Y931C, G935R, R938L, I960V, E985K. (pretreatment and at progression)

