6.6 Prohibited Medications

Subjects must abstain from using prohibited prescription or non-prescription drugs within 7 days or 5 half-lives (whichever is longer) prior to the first dose of study medication and until completion of follow-up procedures (Exclusion Criteria). The following medications are prohibited during the study:

- Any prior or concomitant use of another JAK inhibitor.
- Any investigational medication other than the study drugs.
- Use of the potent inducers of CYP3A4, rifampin and St John's Wart, is not permitted at any time during participation in the study.
- The GM-CSF growth factor receptor agonists must not be used. Preclinical evidence suggest that it is important for CMML proliferation and survival and it is directly upstream for JAK2, the target of ruxolitinib. GM-CSF must not have been used for at least 28 days prior to receiving the first dose of study drug.

7 **Duration of Therapy**

Subjects will be treated for a total of 16 weeks. For subjects responding at week 16, treatment may continue until one of the following criteria applies:

- 7.1 Dose-limiting toxicity is reached,
- 7.2 Inter-current illness that prevents further administration of treatment,
- 7.3 Unacceptable adverse event(s),
- 7.4 Patient decides to withdraw from the study, or
- 7.5 General or specific changes in the patient's condition render the patient unacceptable for further treatment in the judgment of the investigator.
- 7.6 Evidence of disease progression by the IWG 2006 criteria.

Subjects who wish not to continue treatment will complete their end of study visit at week 17. Subjects who were not enrolled in the MTD cohort can increase to the MTD after week 17 if the participant still meets the eligibility criteria. Responding patients will be able to continue until marketing approval of ruxolitinib for CMML.

8 Duration of Follow-Up

Subjects will be followed as per calendar on treatment for 17 weeks. After 17 weeks patient who continue on study will be followed monthly. Off study data on AML transformation and overall survival will be updated every 6 month or until death, whichever occurs first. Subjects removed from study for unacceptable adverse events will be followed until resolution or stabilization of the adverse event.

9 Criteria for Removal from Study

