 - Clinical chemistries including BUN/urea, creatinine, sodium, potassium,
 alkaline phosphatase, alanine aminotransferase (ALT), aspartateaminotransferase
 (AST), , total bilirubin, bicarbonate, calcium, chloride, glucose, LDH, total protein,
 albumin.
 - Urine or serum pregnancy test for females of childbearing potential will be performed at Screening or on Day 1, prior to first dose of study medication.
 Symptom Score using the The Myeloproliferative Neoplasms Symptom Assessment
 - Form (MPN-SAF). (see Appendix D)

Review and record any blood and blood supportive care products for the prior 8 weeks.

- 13.2 Treatment Period (weeks 1-16): Ruxolitinib will be administered as a twice daily oral dose for a 4-week treatment cycle. Subjects will have a CBC with leukocyte differential performed weekly; a blood chemistry will be performed weekly for first cycle and then q 2 weeks. A BM aspirate and biopsy with cytogenetic analysis will be performed after cycle 2 and 4 (weeks 8, 16) to assess pathologic response, cytogenetic response and disease progression. For subjects who achieve CR, marrow CR, or PR a confirmation bone marrow aspirate and biopsy should be obtained 4 to 8 weeks after documentation of CR, marrow CR, or PR.
- 13.3 Week 16 End of Treatment: Subjects will complete a response assessment within one week after their last administration of ruxolitinib. Subjects discontinuing study early should complete their end of treatment visit within two weeks after their last dose of investigational product. Physical exam, vital signs, concomitant medication, adverse event reporting, CBC, and blood chemistry and BM aspirate and biopsy with cytogenetic analysis will be performed.
- Continuation Phase: After completing cycle 4 response assessments, responders may continue to receive ruxolitinib and the final week 16 dose in the absence of DLT or disease progression until marketing approval of ruxolitinib for CMML. Bone marrow biopsy and aspirate will be repeated after every 4 cycles (For subjects who achieve CR, marrow CR, or PR a confirmation bone marrow aspirate and biopsy should be obtained 4 to 8 weeks after documentation of CR, marrow CR, or PR). A CBC will be obtained and complete metabolic profile as per standard of care. The off treatment assessment should be done within a week off treatment.
- 13.5 Off Treatment assessment: includes best response achieved, date of first response, date of loss of response, reason for discontinuation.

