- 13.6 **Off study evaluation**: include vital status, date of death/last contact, transformation to AML and the date of transformation to AML if applicable. This evaluation will be updated every 6 month for 2 years.

Study Calendar	Pre- Study	Wk 1	Wk 2	Wk 3	Wk 4	Wk 5	Wk 6	Wk 7	Wk 8	Wk 9	Wk 10	Wk 11	Wk 12	Wk 13	Wk 14	Wk 15	Wk 16	Wk 17	Weeks 18-48 (if response) Monthly visits	Off-Study or continue if responding as per previous weeks
Ruxolitiniba		X	X	X	X	X	X	X	X	X	X	X	X	X	X	X	X	X	X	X
Informed consent	X		1																	
Demographics	X				71											L				
Medical history	X					X				X				X				X	X	X
Physical exam	X					X				X				X				X	X	X
Vital signs	X					X				X				X				X	X	X
Height	X																			X
Weight	X					X				X				X				X	X	
Performance Status	X					X		N.		X				X				X	X	X
Concurrent medication review	X								М											
CBC w/diff,	X	X	X	X	X	X	X	X	X	X	X	X	X	X	X	X	X	X	X	X
Retic Count	X					X				X				X				X		
Serum chemistry ^b	X	X	X	X	X		X		X		X		X		X		X		X	X
INR, PT, and PTT	X							1		7						7				
Adverse event evaluation		X				events v								-						
Bone marrow biopsy/aspirate ^d ***	X			١,					X	•			Ĭ				X			
B-HCG ^c	X				4															
Lab. Correlates	X	X				X				X				X				X		

Prior CMML	X																			
Treatments																				
Transfusion	X					X				X				X				X	X	X
Log																				
Response										X								X	X	X
Assessments															_					
Symptom Score Scale ^f	X	X	X	X	X	X	X	X	X	X	X	X	X	X	X	X	X	X		
Scale ^f																				
Off-treatment																		X	X	X
Assessment/Off																				
-Study Follow-					7															
-Study Follow- up/ CMML Summary Form																				
Summary Form																				

- a. Dose as assigned for cohort in phase 1, dose assigned as MTD in phase 2
- b: Albumin, alkaline phosphatase, total bilirubin, bicarbonate, BUN, calcium, chloride, creatinine, glucose, LDH, potassium, total protein, AST, ALT, sodium, and total bilirubin.
- c: Serum or urine pregnancy test (women of childbearing potential).
- d: in addition to specimen required for pathologic review, and additional aspirate will be collected (goal volume of 30cc)
- e: in addition to specimen required for routine labs, 6 green top vials, 1 red top vial; on week 1, peripheral blood will be collected twice: at time of first dose, and 3 hours after first dose.

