- f: The Myeloproliferative Neoplasms Symptom Assessment Form (MPN-SAF) using ERT's DiaryPro done by the patient. Data upload and device maintenance will occur at each scheduled visit.

Week 16 Evaluation and End of Treatment: Subjects will complete a response assessment within one week after their last administration of ruxolitinib. Subjects discontinuing study early should complete their end of treatment visit within two weeks after their last dose of investigational product. Physical exam, vital signs, concomitant medication, adverse event reporting, CBC, and blood chemistry and BM aspirate and biopsy with cytogenetic analysis will be performed.

- **Continuation Phase: After completing cycle 4 response assessments, HI-platelet responders may continue to receive ruxolitinib and the final week 16 dose in the absence of DLT or disease progression until marketing approval of ruxolitinib for CMML. Bone marrow biopsy and aspirate will be repeated after every 4 cycles. A CBC will be obtained and complete metabolic profile as per standard of care. The off treatment assessment should be done within a week off treatment.
- *** For subjects who achieve CR, marrow CR, or PR a confirmation bone marrow aspirate and biopsy should be obtained 4 to 8 weeks after documentation of CR, marrow CR, or PR.
- Off Treatment assessment: includes best response, date of first response, date of loss of response, reason for discontinuation.

Off study follow up: include vital status, date of death/last contact, transformation to AML and the date of transformation to AML if applicable. This evaluation will be updated every 6 month for 2 years.

**** all dates are +/- one week

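### The protocol gives inconsistent tests for who stays on ruxolitinib after week 16

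*Combined protocol and SAP*

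**What the plan says.** Four tests apply at week 16.

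- **Response.** Section 7, and the synopsis under Duration of Therapy, set a 16-week course and then state: "For subjects responding at week 16, treatment may continue until one of the following criteria applies". The Continuation Phase text in Section 13 reads: "After completing cycle 4 response assessments, responders may continue to receive ruxolitinib and the final week 16 dose". The calendar column for later visits is headed "Weeks 18-48 (if response) Monthly visits".
- **Clinical benefit.** The synopsis, under Criteria for Removal from Study, states: "Study drug treatment can continue for subjects receiving clinical benefit", subject to the withdrawal criteria. The mandatory-stop list in 9.3, repeated in the synopsis, includes: "No clinical benefit has been attained after 16 weeks of treatment". Section 3.1.2 gives the meaning: "clinical benefit defined as hematologic improvement, complete remission, partial remission, or stable disease".
- **No improvement.** Under 9.1.1, repeated in the synopsis, a subject has completed the study after having "completed 16 weeks of treatment with study medication with no improvement".
- **Platelet response.** The Continuation Phase footnote to the study calendar says: "HI-platelet responders may continue to receive ruxolitinib". It is otherwise essentially the Section 13 sentence, with a lineage added.

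Section 14 and Appendix B define stable disease as less than a PR with no progression over more than 8 weeks. No place says which test prevails.

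**The concern.** Two investigators who both follow the protocol could reach opposite decisions for the same patient at week 16. The decision concerns whether treatment continues, so it matters to patients as well as to the data.

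It also determines what is collected. Subjects who continue have monthly visits and a marrow every four cycles. Subjects off study have six-monthly updates of vital status and AML transformation. Exposure, safety observation on drug and response assessment after week 16 therefore depend on which sentence the site reads.

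Best response may depend on it too. Section 15.1 says phase 2 estimates overall best response, and 15.2 gives no cut-off date for the final count. A subject kept on drug could respond later, and one taken off has less chance to.

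**Working it through.** The plan states no figure on this point, so the check is to apply each test to three kinds of subject at week 16.

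| Test | Stable disease, no improvement | CR, PR, marrow CR, HI-E or HI-N, no platelet response | Platelet responder |
|---|---|---|---|
| Response (Section 7, synopsis, Section 13 text, calendar column) | Not covered, unless stable disease counts as response | May continue | May continue |
| Clinical benefit (synopsis; 9.3 read with 3.1.2) | Can continue; not stopped by this criterion | Can continue | Can continue |
| No improvement (9.1.1, synopsis) | Has completed the study | Not completed by this criterion | Not completed by this criterion |
| HI-platelet (calendar footnote) | Not named | Not named | May continue |

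Marrow CR is not listed in 3.1.2. Without HI it reaches clinical benefit only through the literal stable-disease definition.

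**First column.** The second and third rows conflict whatever responding means. The synopsis holds both under the same heading, Criteria for Removal from Study.

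**Second column.** The Section 13 text and the footnote describe the same continuation phase, and one includes subjects whom the other does not name.

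**Third column.** Platelet responders may continue under every test, which matters for the duration endpoint discussed under the objection.

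**Late best response.** Section 15.2 rejects the drug at 5 or fewer responses among 29, so one added response (5 + 1 = 6) would change the conclusion in a trial sitting at the boundary. This route is open only if stable disease is not itself counted as response. If it is counted, as 3.1.2 reads, the subject is already in the numerator.

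**Illustration of numbers.** The documents give no rates for these categories. The mixes below are assumptions for 29 phase 2 subjects. The formula is 29 × the summed shares, and each test is read as if it alone decided continuation.

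- Low mix (HI-platelet 5%, other response 5%, stable disease 30%):
  - HI-platelet: 29 × 0.05 = 1.45
  - responders: 29 × 0.10 = 2.9
  - clinical benefit: 29 × 0.40 = 11.6
- High mix (15%, 15%, 50%):
  - HI-platelet: 29 × 0.15 = 4.35
  - responders: 29 × 0.30 = 8.7
  - clinical benefit: 29 × 0.80 = 23.2

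Under these mixes the number continuing is about 1 to 4, 3 to 9, or 12 to 23. The figures show only that the tests can select groups of very different size.

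**The case against.** The best defence is that most of these sentences can be read together. Section 7 and the Section 13 text say that responders may continue, and neither says only responders. Section 9.3 is a stop list, and 9.1.1 defines completion and does not govern continuation. No sentence orders a CR, PR, HI-E or HI-N responder off drug at week 16. If response carries the 3.1.2 meaning, responding and clinical benefit coincide. The word HI-platelet may be a stray qualifier: the calendar column says only that there is a response, and the calendar notes themselves ask for confirmatory marrows after CR, marrow CR or PR.

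Much of this stands. It would be wrong to say that Section 7 restricts continuation to responders, or that 9.1.1 is a continuation rule based on any improvement. Two conflicts remain. Reading stable disease as response still leaves 9.1.1 completing the study for a subject whom the synopsis says can continue. The footnote still differs from the Section 13 text. Its qualifier cannot safely be dismissed as a slip, because the same platelet focus appears in the duration-of-response definition in Section 14 and the efficacy analysis in 15.5. Being left unnamed is also not neutral when Section 7 sets a 16-week course and then grants an extension.

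A reader might also infer that the duration endpoints depend on which sentence is used. The documents do not support that:

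- **Duration of response.** Section 14 starts it at a major or complete platelet response, and platelet responders may continue under every test. Stable-disease subjects and non-platelet responders do not enter it as defined.
- **Overall survival and AML transformation.** Sections 8, 10.1 and 13.6 provide for both to be followed off study every six months. The continuation rule reaches them only through exposure.

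Nor can a reader conclude that most subjects still on drug are affected, since no response mix is given.

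**Conclusion.** The inconsistency is real and should be corrected. Subjects with stable disease and no improvement are handled differently by 9.3 and the synopsis on one side and by 9.1.1 on the other. Responders in other lineages are covered by the Section 13 text but not named in the calendar footnote.

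What depends on it is exposure, on-treatment safety follow-up and response assessment after week 16. Late best responses may also depend on it, if stable disease is not counted as response and the final count has no earlier cut-off. The number of subjects affected is unknown, and the counts above rest wholly on assumed mixes. The conclusion that duration of response is unaffected holds for the current Section 14 definition and would need another look if that definition were widened beyond platelet response. No view is taken on which continuation rule is clinically right.

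**What to change.** The sponsor should reconcile these places to one continuation criterion, stated in named IWG categories (CR, PR, marrow CR, HI by lineage, stable disease) and chosen by the clinical team:

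- the synopsis, under both Duration of Therapy and Criteria for Removal from Study;
- Section 7;
- Section 9.1.1;
- Section 9.3;
- the Continuation Phase text in Section 13;
- the calendar column for weeks 18 to 48;
- the Continuation Phase footnote to the calendar.

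Leaving out the synopsis or the calendar column could leave a contradiction standing. The analysis section should add a summary of on-treatment duration by week-16 IWG category, so that a reader can see who continued.

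The cost is wording in eight places, counting the synopsis twice, and one descriptive table. The planned week-16 and week-17 response assessments already supply the categories, and the sample size and decision rule do not change.
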